5.3 Subject screening and registration

Subjects willing to participate in the study will provide written informed consent according to Good Clinical Practice (GCP). Written informed consent must be obtained before any study-related activity.

Upon signing the informed consent, the subject will be registered and assigned a unique subject number. Once a subject number has been assigned, it cannot be reused, and the number stays with the subject even if the subject is subsequently determined to be ineligible for the study.

5.4 Subject withdrawal criteria

Subjects will be withdrawn from the study for the following reasons:

1. The subject withdraws consent at his/her own request or at the request of his/her legally acceptable representative. A subject may decline to participate in the study at any time during the study and without giving particular reasons for his/her decision. In this case, the investigator should make reasonable efforts to ascertain the reason(s), while fully respecting the subject's rights. The subject will not suffer any disadvantage consequently.
2. If, in the investigator's opinion, continuation of study would be harmful to the subject's well-being.
3. In case of unexpected new malignancy (excluding: FL and MZL transformed to lymphoma, MDS transformed to AML and MGUS or SMM transformed to MM) or active inflammatory disease that requires intervention.
4. Lost to follow-up.
5. The consortium discontinues the study.

A subject who discontinues study participation prematurely for any reason after enrolment but before providing the first blood sample will be replaced.

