5.2 Eligibility

5.2.1 Inclusion criteria

Subjects must meet all of the following inclusion criteria to be enrolled in the trial:

General criteria for all study populations:

1. Male and female subjects ≥ 18 years of age;
2. Ability to understand and willingness to sign a written informed consent document.

For patients with hematological malignancies:

1. Patients who have been diagnosed, have measurable disease and / or are being monitored / followed-up due to one of the following conditions: MM, pre-MM conditions (SMM and MGUS), HL, aggressive NHL (DLBCL), FL, MZL, AML, MDS that did not yet undergo any treatment.

NOTE: Patients diagnosed with DLBCL that is transformed from FL or MZL, and patients diagnosed with AML secondary to MDS or MPN, that were treated for their primary disease (FL/MZL/MDS/MPN) prior to study enrollment, are eligible. .

For subjects at risk for developing the investigated hematological malignancies:

1. First degree relatives;
2. Elderly subjects ≥ 65 years of age.

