6.2 Schedule of events

The detailed summary of the evaluations and procedures planned in this study is presented in Tables 2 and 3.

Table 2. Schedule of events

Evaluation	Screening visit¹ (Day -28 to -1)	Baseline sample (Day 1 ± 28 days)	Follow-up visit² (sub-set of patients in Stage 2)
Signed consent form	X		
Assessment of eligibility criteria	X		
Assigning patient ID	X		
Assigning patient barcode	X		
Record medical history ³	X	X	
Record concomitant medications	X	X	X
Record demographics ⁴	X		
Record smoking history / status	X	X	X
Record prior anti-cancer treatments ⁵	X	X	
Record weight	X	X	X
Record heights	X		
Record baseline disease characteristics including prognostic profile ²	X		
MM lab profile for subjects at risk to develop the investigated hematological malignancies ⁶	X		
Blood sampling for central lab (JaxBio) ⁷		X ²	X ²
Disease response evaluation			X ²
Survival status			X
Record adverse events		X	X

¹ Screening visit can be performed at the same day as baseline sample.

² Refer to Table 3 for recommended schedule and disease assessment plan for follow-up patients in Stage 2.

³ Medical history will include details of initial diagnosis.

⁴ Demographics include sex, age and race.

⁵ Only for Secondary-AML, transformed FL and MZL conditions.

⁶ **In Stage 3.** MM lab profile will include SPEP and FLC, full chemistry and CBC.

⁷ Two (2) blood tubes for each sample will be collected and shipped. Refer to Study Manual.

HemaChip tests at the clinical sites ⁸		X ⁹	X ⁹
---	--	----------------	----------------

⁸ **In stages 2 and 3 of the clinical trial only.** The HemaChip and custom reagents will be distributed to partners' labs and all tests will be conducted at the clinical sites.

⁹ Two (2) blood tubes for each sample will be collected. One (1) for test at the clinical sites and the second as a backup for additional validation tests at JaxBio and TAU, as needed. Refer to Study Manual.

Table 3. Recommended schedule and disease assessment plan – Only for follow-up patients

Condition Visit	Baseline Characteristics and Assessments ¹	Follow-up for Disease Evaluation		Blood Sample for Central Lab/HemaChip at site ^{2,3}
		Disease Evaluation ¹	Recommended Schedule	

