7.1 Screening period

- Signed consent form
- Assessment of eligibility criteria
- Assigning patient ID
- Record medical history - Medical history will include details of initial diagnosis
- Record concomitant medications
- Record demographics - sex, age and race
- Record smoking history

- Record prior anti-cancer treatments only for Secondary AML, transformed FL and MZL conditions
- Record weight
- Record height
- Record baseline disease characteristics including prognostic profile - Refer to Table 3 for recommended schedule and disease assessment plan
- MM lab profile - will be performed for subjects at-risk in Stage 3.

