the discovery array and this number of tests should suffice. Accumulation of additional data is expected in the next phases of the project in order to accurately tune the statistical analysis according to the data.

[figure not shown]

Figure 2. Required sample size for HemaChip, analyzed by Proportion sample size determination for binomial distribution (arcsine transformation, significance level = 0.05, test power = 0.8).

Stage 3: Screening at-risk cohorts

When calculating the sample size for the screening stage, the incidences of individual types of hematological malignancies were considered. The assumption is that the individual types will occur in the same proportion also in the risk cohorts of patients. We also consider the minimum number of samples with respect to the HemaChip and its expected sensitivity (as detailed in stage 2), and the known fact that the incidence of the hematological malignancies is about five percent in the risk cohort. Then, the sample population was determined to be approximately 7120. Such a screen is beyond the scope of this project but given that the tests performed side by side with standard diagnosis, the incidence rate is sufficient to derive initial performance metrics based on several hundred tests. Positive results will allow performing a large scale clinical study needed for screening purposes.

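### In Stage 3 the myeloma panel result can be known before the HemaChip sample is drawn, so loss of cases from the analysis set can depend on the reference test

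*Protocol*

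**What the plan says.** Primary objective 4 (Protocol section 2) is the sensitivity and specificity of the test for screening in elderly subjects and first-degree relatives. Section 10.4 expects early performance figures from Stage 3 "given that the tests performed side by side with standard diagnosis".

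The reference work-up is a row of Table 2 (section 6.2): "MM lab profile for subjects at risk to develop the investigated hematological malignancies". A footnote gives its Stage 3 content: "MM lab profile will include SPEP and FLC, full chemistry and CBC". It is marked only in the screening column (Day -28 to -1). Section 7.1 repeats this ("MM lab profile - will be performed for subjects at-risk in Stage 3"), and section 7.2 does not list the panel. The HemaChip tubes belong to the baseline column (Day 1 ± 28 days) and to section 7.2. The two visits may coincide, but need not: "Screening visit can be performed at the same day as baseline sample".

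Three other rules act on the interval between them:

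- **Replacement (5.4):** "A subject who discontinues study participation prematurely for any reason after enrolment but before providing the first blood sample will be replaced".
- **Withdrawal criterion 3 (5.4):** subjects are withdrawn "In case of unexpected new malignancy (excluding: FL and MZL transformed to lymphoma, MDS transformed to AML and MGUS or SMM transformed to MM"), or for active inflammatory disease needing intervention.
- **Analysis set (10.2.1):** eligible, consented subjects who gave at least one blood sample.

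No section withholds the panel result until the HemaChip draw, says how an at-risk subject with an abnormal panel is handled, or asks for pre-draw leavers to be reported by panel result.

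**The concern.** In an accuracy study, entry to the analysis should not depend on the reference result. Here the reference test may be done and reported first, and the index sample is what admits a subject to the analysis set. A subject told of an abnormal protein result may go for work-up and not return for the study draw. The investigator may judge the subject unsuitable under exclusion criterion 6. If myeloma itself is found, withdrawal criterion 3 exempts precursors that transform to myeloma, but on a plain reading does not exempt myeloma newly found in an at-risk subject.

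Sensitivity is estimated among cases only, and Stage 3 has few of them. If the cases that leave differ from those that stay, for example because they are more overt, the estimate is biased as well as less precise. At-risk subjects give blood once and their participation then ends (sections 4.4 and 6.1), so no later visit recovers a lost case.

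**Working it through.** **Inputs from the protocol.** Screening window Day -28 to -1; baseline window Day 1 ± 28 days; same-day visits optional (Table 2). Stage 3 size 400 + 500 = 900 (section 4.3). Rate of hematological malignancy in the risk cohort 5%; expected value 0.85 against 0.80, significance level 0.05, power 0.80, arcsine method (section 10.4). **Not given:** any rate of leaving before the draw. The shares below are assumptions.

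**1. The plan's own Stage 3 figure.** n = [(z_alpha + z_power) / (2·asin√0.85 − 2·asin√0.80)]². With one-sided 0.05 this is 355.4, rounded up to 356, which matches. (Two-sided gives 451.2, rounded up to 452, which does not.) Then 356 / 0.05 = 7120, the stated screening population. So the plan does apply the 5% as the case rate in the at-risk cohort.

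**2. Gap between panel and draw.** Day -28 to Day 1 is 28 days if there is no Day 0. Adding the 28-day allowance gives 28 + 28 = 56 days as the literal maximum (57 if a Day 0 is counted). If screening is read as anchored to the actual draw, the maximum is about 28 days. With a same-day visit the gap is 0.

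**3. Expected cases.** 400 × 0.05 = 20; 500 × 0.05 = 25; total 45. Let f be the share of cases leaving before the draw, with the cohort refilled to 900 from the same pool. Cases remaining = 900 × 0.05(1 − f) / (1 − 0.05f). The interval is the Wilson 95% interval at sensitivity 0.85.

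| f (assumed) | Cases | 95% interval |
|---|---|---|
| 0 | 45.0 | 0.719-0.926 |
| 20% | 36.4 | 0.701-0.932 |
| 50% | 23.1 | 0.656-0.944 |

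**4. What replacement does.** At f = 50% without any refill, 45 × 0.5 = 22.5 cases remain, against 23.1 with refill. Replacement therefore adds slightly to the case count. It does restore the total to 900, so the headcount gives no sign of the loss.

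**5. Bias, illustration only.** Assume half the cases are overt with sensitivity 0.95 and half are precursors with 0.75, so the true value is 0.85. If a share g of overt cases leaves, observed sensitivity = [0.5(1 − g)·0.95 + 0.5·0.75] / [0.5(1 − g) + 0.5].

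- g = 20%: (0.380 + 0.375) / 0.90 = 0.839
- g = 50%: (0.2375 + 0.375) / 0.75 = 0.817
- g = 100%: 0.375 / 0.50 = 0.750

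**The case against.** Four readings go further than the documents allow.

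- **That replacement swaps cases for non-cases and so removes the numerator.** It does not. The loss comes from leaving before the draw, and adding panel-negative subjects leaves sensitivity unchanged (step 4). What stands against the rule is only that it conceals the loss.
- **That panel-positive subjects are moved to the Stage 2 disease groups.** The patient criterion in 5.2.1 covers people who "have measurable disease and / or are being monitored / followed-up due to one of the following conditions: MM, pre-MM conditions (SMM and MGUS"), so someone newly diagnosed and untreated could fit it. But no section prescribes a transfer, and an abnormal panel is neither an exclusion criterion nor, alone, a diagnosis: Table 3 lists marrow findings and FISH under plasma cell disease. Transfer is possible, not planned.
- **That section 10.4 contradicts Table 2.** Testing side by side can mean both tests in the same people. It does not have to mean the same day.
- **That a gap of 56 days is to be expected.** It needs both windows at opposite extremes. The ± 28 days would also allow the draw to come first.

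The defence has further points. Amendment 2 explains the Stage 3 panel as a way to evaluate screening accuracy better, so the sponsor evidently wants panel-positive subjects in the analysis. Section 10.4 already calls a fully powered screen out of scope. The word unexpected in criterion 3 could be argued not to cover myeloma in a cohort screened for it, and a finding of MGUS or SMM does not clearly trigger that criterion. The first blood sample in 5.4 is undefined; if the panel tube counted, replacement would not apply, though the subject would still have no HemaChip result.

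All of this limits the size and the likelihood. It does not remove the sequence: reference result first, index sample later, and entry to the analysis decided by the index sample. The stated purpose of the panel makes closing the gap more worthwhile.

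**Conclusion.** The point holds as a gap in the Stage 3 schedule. The protocol permits the myeloma panel to be known before the HemaChip draw, and subjects who leave in between fall out of the analysis set. Loss of cases can then depend on the reference result, which may bias the sensitivity estimate for primary objective 4 and make it less precise.

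The size cannot be derived from the documents. The fall from 45 to about 23 cases rests on an assumed 50% loss. The 5% covers all hematological malignancies while the panel targets myeloma and its precursors, so 45 is an upper scale. Even then the interval widens only moderately. Bias is the greater worry, but its amount and direction depend on who leaves, and the mix in step 5 is assumed. Sites that use same-day visits have no gap. This is a cheap improvement to a primary objective, not a fault that invalidates the stage.

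**What to change.** For Stage 3 only:

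1. In Table 2 footnote 1 and sections 7.1/7.2, require the HemaChip tubes to be drawn at the same visit as the myeloma panel, or at least before its result is available.
2. State that a sampled at-risk subject with an abnormal panel stays in the Stage 3 analysis set and is not counted toward the patient groups in Table 1.
3. Report any subject who leaves between panel and draw by panel result. Without a HemaChip result they cannot enter the sensitivity estimate, but the reader can then judge the selection. Subject numbers are never reused (section 5.3), so they remain traceable.
4. Reconcile withdrawal criterion 3 in section 5.4 with the purpose of Stage 3, so that it is clear what happens when a malignancy under study is found in an at-risk subject. Section 11.5 already allows use of samples taken before discontinuation, so an early draw protects the data however this is settled.

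The cost is protocol wording plus one disposition table. No visit or procedure is added, since same-day sampling is already allowed. The downside is a few tubes drawn from subjects later found ineligible.

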5.5 Enrollment restrictions

The consortium may increase the number of samples and/or stop analysis of a specific subgroup depending on the analysis results throughout the trial conduct period.

6 DESIGN & TREATMENT PLAN

6.1 Duration of participation

Follow-up patients with hematological cancers will be followed for treatment for the disease, disease response and survival status for up to 36 months, unless they terminate early due to meeting one of the withdrawal criteria.

Subjects that serve as controls, subjects at risk (from the Third stage) and a subset of patients from the First and Second stage are expected to donate blood a single time. Following this donation, their participation will end.

Subjects who complete the main study, may be followed up for their disease status, anti-cancer treatments, concomitant medications, new primary malignancy and survival, following statistical review of the study results. A serial blood samplings will be performed during the long term follow-up according to the standard clinical practice and/or recommended schedule and disease assessment plan (see Table 3).

A detailed plan for long term follow-up beyond the main study will be provided as an amendment to this protocol.

6.2 Schedule of events

The detailed summary of the evaluations and procedures planned in this study is presented in Tables 2 and 3.

Table 2. Schedule of events

Evaluation	Screening visit¹ (Day -28 to -1)	Baseline sample (Day 1 ± 28 days)	Follow-up visit² (sub-set of patients in Stage 2)
Signed consent form	X		
Assessment of eligibility criteria	X		
Assigning patient ID	X		
Assigning patient barcode	X		
Record medical history ³	X	X	
Record concomitant medications	X	X	X
Record demographics ⁴	X		
Record smoking history / status	X	X	X
Record prior anti-cancer treatments ⁵	X	X	
Record weight	X	X	X
Record heights	X		
Record baseline disease characteristics including prognostic profile ²	X		
MM lab profile for subjects at risk to develop the investigated hematological malignancies ⁶	X		
Blood sampling for central lab (JaxBio) ⁷		X ²	X ²
Disease response evaluation			X ²
Survival status			X
Record adverse events		X	X

¹ Screening visit can be performed at the same day as baseline sample.

² Refer to Table 3 for recommended schedule and disease assessment plan for follow-up patients in Stage 2.

³ Medical history will include details of initial diagnosis.

⁴ Demographics include sex, age and race.

⁵ Only for Secondary-AML, transformed FL and MZL conditions.

⁶ **In Stage 3.** MM lab profile will include SPEP and FLC, full chemistry and CBC.

⁷ Two (2) blood tubes for each sample will be collected and shipped. Refer to Study Manual.

HemaChip tests at the clinical sites ⁸		X ⁹	X ⁹
---	--	----------------	----------------

⁸ **In stages 2 and 3 of the clinical trial only.** The HemaChip and custom reagents will be distributed to partners' labs and all tests will be conducted at the clinical sites.

⁹ Two (2) blood tubes for each sample will be collected. One (1) for test at the clinical sites and the second as a backup for additional validation tests at JaxBio and TAU, as needed. Refer to Study Manual.

Table 3. Recommended schedule and disease assessment plan – Only for follow-up patients

Condition Visit	Baseline Characteristics and Assessments ¹	Follow-up for Disease Evaluation		Blood Sample for Central Lab/HemaChip at site ^{2,3}
		Disease Evaluation ¹	Recommended Schedule	
MM	
 1. PCD diagnosis⁴ 2. Chemistry⁵ 3. Blood count⁶ 4. Virology⁷ 5. MM lab profile⁸ 6. Other baseline assessments⁹ 	
 1. Response will be evaluated according to IMWG criteria¹⁰ 2. MM lab profile⁸ 	MGUS: Once every 6 months SMM: Once every 3-6 months MM: Once every 2 months	X
HL, DLBCL, FL, MZL	
 1. Disease diagnosis¹¹ 2. Chemistry¹² 3. Blood count¹³ 4. Virology⁷ 5. Disease evaluation¹⁴ 6. Other baseline assessments¹⁵ 	
 1. Response will be evaluated according to Lugano 2014 criteria 2. Assessment of response^{14,16} 3. Assessment of B Symptoms 	
 1. First 2 Years: every 3 months 2. From the 3rd year: every 6 months 	X
AML	
 1. AML diagnosis¹⁷ 2. Chemistry¹⁸ 3. Blood count and smear¹⁹ 4. Coagulation tests²⁰ 5. Virology²¹ 6. Other baseline assessments²² 	
 1. Response will be evaluated according to ELN guidelines 2017/2022²³ 2. Molecular MRD when evaluable²³ 3. Blood count and chemistry 	
 1. Intensive chemotherapy 
 a. Day14 assessment²⁴ b. 3-5 weeks after induction therapy upon hematologic recovery c. Optional – upon hematologic recovery following each consolidation cycle d. If ASCT: 1 month after therapy 	X

¹ Will be performed locally at the clinical site.

² **In stage 1 of the clinical trial only**, Two (2) blood tubes for each sample will be collected in STRECK tube and sent to central lab (JaxBio). Refer to Study Manual. **In stages 2 and 3 of the clinical trial**, the HemaChip and custom reagents will be distributed to partners' labs and all tests will be conducted at the clinical sites. Two (2) blood tube for each sample will be collected, one (1) for test at the clinical sites and the second as a backup for additional validation tests at JaxBio and TAU, as needed.

³ Blood samples for Blood Sample for Central Lab/HemaChip at site – at diagnosis (baseline) and at all disease evaluation follow-up visits.

⁴ PCD diagnosis – date and age at diagnosis, type, ISS, R-ISS, BM Aspirate/Biopsy %PCs, FISH

⁵ Chemistry includes: albumin, blood urea nitrogen (BUN), creatinine, glucose, uric acid, calcium, chloride, phosphorus, potassium, sodium, lactate dehydrogenase (LDH), total protein, magnesium, alkaline phosphatase, alanine aminotransferase (ALT), aspartate aminotransferase (AST), total bilirubin, β 2 microglobulin.

⁶ Blood Count: Hemoglobin, hematocrit, white blood cells (WBCs) with complete manual or automated differential (total neutrophils, lymphocytes, monocytes, eosinophils, basophils; absolute or percentage will be acceptable), red blood cells (RBCs), platelet count.

⁷ Virology: Anti HCV, HBs Antigen, HBs ab, Anti-HBc, HIV.

⁸ MM lab profile: M-protein by serum protein electrophoresis (SPEP) and immunofixation (immunofixation is required at baseline and to confirm CR regardless of whether measurable M-protein was present at baseline), Urine M -protein electrophoresis (UPEP) and urine immunofixation (requires 24-hour urine collection) only if patient has disease measurable by UPEP at baseline (Screening value ≥ 200 mg/24 hours) but not by serum free light chain (sFLC), sFLC (regardless if the patient had measurable disease at baseline), qIgA levels in patients with immunoglobulin A (IgA) type MM only.

⁹ Other baseline assessments – bone marrow involvement, extramedullary disease.

¹⁰ Refer to Appendix 2

¹¹ Disease diagnosis – date, age, stage (per to Ann Arbor, see Appendix 3), **for HL only** – early favorable/early unfavorable/advanced (including IPS), **for FL only** – FLIPI score

¹² Chemistry: Albumin, lactate dehydrogenase (LDH), β 2 microglobulin.

¹³ Blood count: Hemoglobin, hematocrit, white blood cells (WBCs) with complete manual or automated differential (total neutrophils, lymphocytes, monocytes, eosinophils, basophils; absolute or percentage will be acceptable), red blood cells (RBCs), platelet count

¹⁴ Assessments to include disease burden and symptoms, staging, CT, FDG PET, PE, bone marrow aspirate + biopsy (in the event of CR for participants who do not have PETFDG avid lymphoma). No further PET scans are required for NHL, which are not FDG-avid at baseline, unless clinically indicated. For FDG-avid NHL, PET is required at baseline, Weeks 12 and 24, to confirm CR or as clinically indicated.

¹⁵ Other baseline assessments – bone marrow involvement, extranodal disease, nodal sites, B-symptoms.

¹⁶ Refer to Appendix 4.

¹⁷ AML diagnosis – date and age at diagnosis, AML type (de novo VS secondary to MDS/MPN/therapy related), AML risk stratification (ELN 2022), BM Aspirate/Biopsy – % blast cells, cytogenetics, FISH, FACS, molecular testing.

¹⁸ Chemistry includes: albumin, blood urea nitrogen (BUN), creatinine, glucose, uric acid, calcium, chloride, phosphorus, potassium, sodium, lactate dehydrogenase (LDH), total protein, magnesium, alkaline phosphatase, alanine aminotransferase (ALT), aspartate aminotransferase (AST), total bilirubin.

¹⁹ Blood Count and smear: Hemoglobin, hematocrit, white blood cells (WBCs) with complete manual or automated differential (total neutrophils, lymphocytes, monocytes, eosinophils, basophils; absolute or percentage will be acceptable), red blood cells (RBCs), platelet count. % peripheral blast cells on smear.

²⁰ Coagulation tests: PT, PTT, INR, fibrinogen.

²¹ Virology: Anti HCV, HBs Antigen, HBs ab, Anti-HBc, HIV.

²² Other baseline assessments – extramedullary disease.

			
 e. After completing therapy: every 3 months for 2 years, and every 6 months from 3rd year, or as guided in selected treatment protocol 
2. Low-intensity chemotherapy:
 
 a. First response assessment as guided in selected protocol b. Every 3-6 months 	
--	--	--	--	--

²³ Refer to Appendix 5.

²⁴ Day 14 assessment: according to routine per site, if assessed mention %blasts or MLFS (morphologic leukemia free state).

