7 STUDY ASSESSMENTS

This section details the tests and the assessments that will be performed during the study (36 months).

AEs of special interest, (serious) AEs related to study procedures, concomitant medications, second primary malignancies and anti-cancer treatments will be collected from the time of signing of ICF until completion of the clinical trial.

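### The baseline sampling window does not require the draw to precede first anti-cancer treatment, which conflicts with the protocol's own description of baseline as the sample at diagnosis

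*Protocol*

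**What the plan says.** The protocol describes baseline in several places.

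- **Table 2 (6.2)** gives the window as "Baseline sample (Day 1 ± 28 days". Screening runs from Day -28 to Day -1, and a footnote adds: "Screening visit can be performed at the same day as baseline sample". Eligibility is ticked at screening only. Day 1 is not defined.
- **Inclusion criteria (5.2.1)** ask for patients with one of the listed conditions "that did not yet undergo any treatment". A NOTE makes an exception for DLBCL transformed from FL or MZL and for AML secondary to MDS or MPN: patients "that were treated for their primary disease (FL/MZL/MDS/MPN) prior to study enrollment, are eligible".
- **Table 3, footnote 3**, which covers follow-up patients, times the research samples "at diagnosis (baseline) and at all disease evaluation follow-up visits".
- **Interim analysis (10.3)** refers to newly diagnosed NHL and MM samples.
- **Recording of treatment.** In Table 2, prior anti-cancer treatment is recorded at screening and at the baseline sample, but "Only for Secondary-AML, transformed FL and MZL conditions". Section 7 adds that "second primary malignancies and anti-cancer treatments will be collected from the time of signing of ICF until completion of the clinical trial".
- **Analysis population (10.2.1)** takes every eligible, consented patient with at least one blood sample. Treatment status at the draw plays no part.

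**The concern.** The baseline sample carries most of the study. It supplies the markers in Stage 1, the sensitivity in Stage 2, and the pre-treatment measurement for predicting response. Each use assumes that the sample shows untreated disease. The protocol makes untreated status a condition of entry but not of the draw, and then allows up to 28 days after Day 1 for the draw.

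A sample taken on treatment could weaken the disease signal and lower sensitivity. It could also let the panel pick up treatment effects, which might raise apparent detection. The direction is therefore not known in advance.

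The loss cannot always be repaired at analysis. Sections 4.4 and 6.1 say that a subset of Stage 1 and Stage 2 patients donates only once. The backup tube comes from the same draw. Section 5.4 replaces only subjects who leave before giving a first sample. A pre-treatment sample that was never drawn cannot be recovered.

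**Working it through.** **Does the text allow a treated baseline sample?**

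1. Eligibility, including untreated status, is assessed at screening, as early as Day -28.
2. The draw may be as late as 28 days after Day 1. Screening and draw can lie about eight weeks apart (28 + 28 = 56 days).
3. If Day 1 is enrolment, treatment can begin in the following four weeks and the draw is still in window. If Day 1 is diagnosis, the same holds. If Day 1 is the start of treatment, the whole later side of the window is on treatment. No reading that gives the later side any content excludes a treated draw.
4. Section 10.2.1 keeps such a sample in the analysis.
5. Table 3 footnote 3 and section 10.3 describe baseline as at diagnosis or newly diagnosed. Table 2 guarantees neither.

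**The protocol's own sample sizes (10.4).** Inputs are null sensitivity p0 = 0.80, alpha 0.05 and power 0.80. The one-sample arcsine formula is

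n = [(z_alpha + z_power) / (2·asin√p1 − 2·asin√p0)]²

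With one-sided alpha, z_alpha + z_power = 1.645 + 0.842 = 2.486 (from unrounded values).

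- p1 = 0.95: (2.486 / 0.4763)² = 27.3, so 28 (stated 30)
- p1 = 0.89: (2.486 / 0.2512)² = 98.0, just above 98, so 99 (stated 99)
- p1 = 0.85: (2.486 / 0.1319)² = 355.4, so 356 (stated 356)

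The plan's figures reproduce, with 30 a rounded-up 28. Sidedness is not stated; two-sided alpha would give 35, 125 and 452.

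**What exposed samples could do.** The documents give neither the share of exposed samples (f) nor the loss of sensitivity in them (d). Both are assumed below. Observed sensitivity is p − f·d, and power is Φ[(2·asin√p_obs − 2·asin√0.80)·√n − 1.645].

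Stage 1, n = 30, true sensitivity 0.95:

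| Exposed share | Loss in exposed samples | Observed sensitivity | Power at 30 | n for 80% power |
|---|---|---|---|---|
| none | – | 0.95 | 0.83 | 28 |
| 5% | 10 points | 0.945 | 0.80 | 31 |
| 10% | 20 points | 0.93 | 0.69 | 41 |
| 20% | 20 points | 0.91 | 0.54 | 62 |
| 20% | 40 points | 0.87 | 0.27 | 173 |

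Stage 2, a group of 100 with true sensitivity 0.89: power is 0.81 with no exposure and 0.60 with 10% exposed at 20 points lower.

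A harsher illustration uses the 85% assumed for validation and supposes that detection is halved in exposed samples:

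- 10% exposed: 0.9 × 0.85 + 0.1 × 0.425 = 0.8075
- 20% exposed: 0.8 × 0.85 + 0.2 × 0.425 = 0.765
- The 5-point margin over 80% is used up at f = 0.05 / 0.425, about 12%.

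All these cases model dilution only.

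**The case against.** The best defence is that the authors meant baseline to be untreated. Inclusion requires it, footnote 3 says at diagnosis, and 10.3 says newly diagnosed. Recording prior treatment at the baseline visit only for the exception groups makes sense only if nobody else was expected to be on treatment by then. Table 2 also serves controls and at-risk subjects, who have no therapy, so its Day 1 is unlikely to mean first dose. Because anti-cancer treatment is collected from consent, exposed samples could be identified and set aside.

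Most of this stands as evidence of intent. It does not put a condition on the draw. Flagging a sample afterwards does not supply the missing pre-treatment one. Draw timing is set by the protocol, so a statistical analysis plan (not among the documents reviewed) could not restore it.

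Three stronger readings are tempting and are not supported.

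- **AML samples after disease clearance.** Table 3 schedules AML assessments at day 14 and "3-5 weeks after induction therapy upon hematologic recovery". A reader might infer that a compliant baseline could fall after clearance. That needs Day 1 to be at or near the start of treatment, which the protocol never says. Footnote 3 also lists the diagnosis sample separately from the evaluation visits.
- **Treated AML and DLBCL patients pooled into the signature.** The NOTE is an open exception limited to secondary AML and transformed DLBCL treated for the antecedent disease, and that treatment is recorded. Table 1 has one AML and one DLBCL row, but no pooled analysis is stated, and stratification may be left to the analysis plan. Whether these patients should be left out of Stage 1 is debatable, since they have the target diseases.
- **A known loss of sensitivity.** The window permits exposure; it does not show that exposure will occur, how often, or with what effect.

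**Conclusion.** The point holds as a gap in a stated rule and an inconsistency between sections. Table 2 permits a baseline draw after treatment starts, and Table 3 footnote 3 and section 10.3 describe something else; the passages must be reconciled.

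The effect on marker selection and sensitivity cannot be derived from the documents. Across the assumed cases tabulated for Stage 1, power ranges from nearly unchanged (0.80 against 0.83) to 0.27. The 80.8% and 76.5% results are illustrations that rest on halved detection and on assumed exposure shares of 10% and 20%. They are not estimates. The change is worth making because it is cheap and the missing sample cannot be replaced, not because a particular loss has been shown.

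**What to change.** 1. Define Day 1 in Table 2.
2. In Table 2 and section 7.2, require the research baseline sample before the first anti-cancer treatment for the disease under study. Record the draw date relative to that treatment.
3. Classify any later draw as a follow-up sample. Leave it out of Stage 1 marker selection and the Stage 2 sensitivity estimate.
4. Bring Table 2, Table 3 footnote 3 and section 10.3 to one description of baseline.
5. Separately, for secondary AML and transformed DLBCL previously treated for the antecedent disease, use the prior-treatment field already collected. Report their sensitivity as its own stratum, and repeat marker selection without them as a sensitivity analysis.

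This is a short amendment to research sampling and analysis. It does not touch patient care. The downside is that a few late-sampled patients do not count toward the group sizes and may need to be made up by further recruitment.
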